5.3 SUBJECT POPULATION(S) FOR ANALYSIS	12
6 SAFETY AND ADVERSE EVENTS	12
7 DATA HANDLING AND RECORD KEEPING	13
7.1 CONFIDENTIALITY.....	13
7.2 SOURCE DOCUMENTS.....	13
7.3 RECORDS RETENTION	14
8 STUDY MONITORING, AUDITING, AND INSPECTING	14
8.1 STUDY MONITORING PLAN	14
8.2 AUDITING AND INSPECTING	15
9 ETHICAL CONSIDERATIONS.....	15
10 STUDY FINANCES	15
10.1 FUNDING SOURCE	15
11 PUBLICATION PLAN	15

12	REFERENCES	15
13	ATTACHMENTS	ERROR! BOOKMARK NOT DEFINED.

LIST OF ABBREVIATIONS

CFR	Code of Federal Regulations
CRF	Case Report Form
DSMB	Data and Safety Monitoring Board
FDA	Food and Drug Administration
GCP	Good Clinical Practice
HIPAA	Health Insurance Portability and Accountability Act
IRB	Institutional Review Board
PHI	Protected Health Information
PI	Principal Investigator
SAE	Serious Adverse Event/Serious Adverse Experience
SOE	Schedule of Events
SOP	Standard Operating Procedure
IQR/M	Interquartile Range/Median

Study Summary

Title	A Prospective Study of the Role and Accuracy of Consumer-Facing Wearable Technology for Patient Monitoring in Gastrointestinal Endoscopy
Running Title	Wearable Technology Endoscopy
Title Acronym	Wearable Tech
IRB Protocol Number	21-007738
Phase	Prospective study
Methodology	Subjects who are eligible will have two consumer-facing wearable smart devices placed before scheduled endoscopy. Data from the devices will be downloaded after the procedure and analyzed. Patients and providers will complete a survey regarding their experience.
Overall Study Duration	6 months Recruitment and Active study execution, 3 months analysis and 3 months publication. Total: 12 months
Subject Participation Duration	Up to 60 days screening prior to study procedure, duration of the procedure itself, and completion of a survey within 14 days of procedure date
Objectives	Measure the accuracy and safety of wearable technology in patients undergoing endoscopic gastrointestinal procedures with sedation. Assess patient and provider preferences regarding wearable technology.
Number of Subjects	Five hundred (500)
Diagnosis and Main Inclusion Criteria	Subjects over 18 years of age who are scheduled to undergo an endoscopic procedure with sedation
Study Device	Consumer-facing wearable smart devices(examples include Apple Watch Series 6, FitBit Versa, The QardioCore ECG ambulatory monitoring device)
Reference Modality	Sedation/Anesthesia record
Statistical Methodology	All continuous variables will be expressed as mean and standard deviation. Categorical variables will be expressed as percentages.

1 Introduction

This document is a clinical research protocol relating to a prospective study of the role and accuracy of consumer-facing wearable technology in gastrointestinal endoscopy. The described study will be conducted in compliance with this protocol, applicable United States government regulations and Mayo Clinic policies and procedures.

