1.4 Study Rationale and Risk Analysis (Risks to Benefits Ratio)

1.4.1 Study Rationale

We hope to further characterize and define the role of consumer-facing technology in the clinical environment by focusing on device accuracy when compared to standard clinical monitoring in patients undergoing an endoscopic procedure. We will generate and answer questions related to these devices that have not yet been explored in the gastroenterology literature. We will provide a timely and much-needed framework that addresses both practical and theoretical considerations around a technology that has become increasingly relevant to patients.

This study will specifically address whether consumer facing wearable devices can serve as patient monitoring devices in a comparable manner to the current gold standard in the procedural suite. In addition to accuracy, we will assess whether certain procedural maneuvers interfere with device data collection. This information will be relevant to patients, providers and healthcare institutions and can help inform policy regarding these devices.

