3.1 General Design

We will perform a prospective, non-blinded, exploratory study to assess the accuracy and safety of smart technology in the endoscopy suite for patients undergoing gastrointestinal endoscopic procedures with sedation. We will also simultaneously perform an assessment of patient and provider preferences using narrative-driven, qualitative evaluation.

Patients will be identified by reviewing daily procedure listings on endoscopy units on Alfred 6, Gonda 2 and Gonda 9. Recruitment will occur over the phone the day prior to a procedure, or the pre-procedure areas on the day of the procedure. Patients who meet inclusion criteria and consent to participation in the study will be provided the smart devices. The devices will be secured to the wrist and torso by study personnel prior to administration of sedatives. The smart watch will be programmed to record respiratory rate, heart rate, and oximetry using native, first party device applications. These applications include *Blood Oxygen* (measures oxygen saturation), *ECG* (records single lead ECG), *Heart Rate* (heart rate), and *Health* (which logs respiratory rate while sleeping). The QardioCore ECG device will measure a single-lead ECG, heart rate, skin temperature, and respiratory rate.

The patient will undergo his or her scheduled procedure. Patients, proceduralists and anesthetists will not be blinded to their enrollment as the devices will be visible. On completion of the procedure, the devices will be removed by the study coordinator and data downloaded onto a central device for analysis. Procedural information will be extracted from the operative note, sedation record, and anesthesia encounter in EPIC. The day after the patient's procedure, a survey will be submitted to them electronically which will remain open until 14 days after

the procedure. Aen electronic reminder will be sent if uncompleted at 7 days, followed by a telephone reminder if not completed at 13 days. There will be no additional patient follow up after completion of the survey. At study completion, a survey will be sent to involved proceduralists and anesthetists.

3.2

Figure 1: Study Design

[figure not shown]

Table 1. Schedule of Events

	Baseline Screening & Enrollment Visit 1 Days -60 to 0	Accrual: Study Intervention Visit 2 Day 0	Patient Survey Visit 3 Day +1 to +14	Provider survey Days 0 to 180
Inclusion/ Exclusion	X	X (if not performed earlier)		
Device(s) Placement/ Recording		X		
Patient Survey			X	

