5.2 Statistical Methods

Descriptive Statistics

Baseline values for demographic, clinical, and outcome will be tabulated for the study subjects. Continuous variables will be expressed as mean and standard deviation. Categorical variables will be expressed as percentages.

We will measure the rate of concordance between device detection and documentation in anesthesia record (# of events recorded on wearable device / events noted on anesthesia record). Events to be recorded include tachycardia (HR > 100), bradycardia (HR < 60), desaturation (peripheral O₂ saturation < 88%), any arrhythmia, and tachypnea (RR > 18).

We will also calculate the difference in maximum and minimum heart rate, respiratory rate, and oxygen saturation recorded by the watch compared to the sedation record.

Handling of Missing Data

Subjects with missing or incomplete data will be noted but will not include in the final analysis. Available information regarding these patients will be reported separately to allow for evaluation of external validity

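### The Section 5.2 concordance ratio counts device and charted events without pairing them in time, so late or unrelated device events score as full detections and the monitoring claim in Section 1.4.1 is not supported by these outputs alone

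*Combined protocol and SAP*

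**What the plan says.** The wide question is in Section 1.4.1: "This study will specifically address whether consumer facing wearable devices can serve as patient monitoring devices in a comparable manner to the current gold standard". The primary objective in Section 2.1 is narrower. It concerns accuracy for monitoring relative to the equipment now in use, and it does not name timeliness. Section 3.1 calls the study exploratory, and Section 5.1 calls it descriptive with no testing planned.

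On data capture, the Methodology row of the Study Summary reads: "Data from the devices will be downloaded after the procedure and analyzed". Section 3.1 gives the same order of steps in more detail: "On completion of the procedure, the devices will be removed by the study coordinator and data downloaded onto a central device for analysis". The reference is the sedation or anesthesia record (Study Summary).

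Section 5.2 gives two accuracy measures.

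- The first is concordance: "We will measure the rate of concordance between device detection and documentation in anesthesia record". It is defined as the number "of events recorded on wearable device / events noted on anesthesia record". Five event types are counted. Four are defined by a cut-off on heart rate, saturation or respiratory rate, and the fifth is any arrhythmia. None has an onset time or minimum duration.
- The second concerns extremes: for heart rate, respiratory rate and saturation, the highest and lowest watch values are each set against those in the sedation record and the difference is taken.

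The documents do not mention clock alignment, a rule for pairing a device event with a charted one, a matching window, detection delay, or any assessment of live display or alarms. They give neither the charting interval nor the device logging interval, and they do not say whether exported readings carry timestamps.

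**The concern.** A monitor is useful only if it shows the right event at about the right time. A ratio of two totals does not check either part. The device total can include events logged well after the charted one, and events that correspond to nothing in the record. The difference in extremes has a similar gap, because the same peak or trough recorded later in the procedure gives the same difference.

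Following the plan exactly could therefore produce full concordance for a device whose events are late or partly spurious. A reader of the results, with Section 1.4.1 in mind, could take that figure as support for using the device as a monitor, which these measures do not test.

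Section 1.4.1 also promises to look at whether procedural maneuvers disturb device recording. Linking a gap in the recording to a maneuver needs a common time base, and the plan does not provide one.

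**Working it through.** **No figure to reproduce.** The plan gives no expected concordance, margin or precision. The target of 500 subjects has no derivation. The check is therefore of how the stated measures behave.

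**Inputs.** From Section 5.2: concordance C = D / R, where D is the number of device events and R the number of charted events. Everything else is assumed for illustration: R = 100 charted events spaced well apart, device delays of 0 to 300 seconds, and matching windows of 15 to 300 seconds.

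**Step 1: a pure delay.** Shift every device event later by the same amount. D stays at 100, so C = 100 / 100 = 1.00 at any delay. Compare this with M, the proportion of charted events followed by a device event within w seconds:

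| Delay (s) | C (Section 5.2) | M, w = 15 | M, w = 30 | M, w = 60 | M, w = 120 | M, w = 300 |
|---|---|---|---|---|---|---|
| 0 | 1.00 | 1.00 | 1.00 | 1.00 | 1.00 | 1.00 |
| 30 | 1.00 | 0.00 | 1.00 | 1.00 | 1.00 | 1.00 |
| 60 | 1.00 | 0.00 | 0.00 | 1.00 | 1.00 | 1.00 |
| 120 | 1.00 | 0.00 | 0.00 | 0.00 | 1.00 | 1.00 |
| 300 | 1.00 | 0.00 | 0.00 | 0.00 | 0.00 | 1.00 |

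**Step 2: late and unrelated events together.** Suppose the device logs 60 prompt events, 20 events five minutes late, and 20 events that match nothing charted.

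- C = (60 + 20 + 20) / 100 = 1.00.
- M with a 60-second window = 60 / 100 = 0.60.
- M with a 300-second window = (60 + 20) / 100 = 0.80.

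C can also exceed 1. With 90 true detections and 20 unrelated events, C = (90 + 20) / 100 = 1.10.

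**Step 3: extremes.** A procedure's maximum or minimum does not depend on when it occurred. If the device records the same extreme later but still within the procedure, the Section 5.2 difference is unchanged.

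**Step 4: sparse logging.** Let a device log one value every k minutes, and let an event last d minutes with onset at a random time.

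- If d is at least k, the event is always caught, with mean delay k / 2. This is 0.5 minutes at k = 1, 2.5 at k = 5 and 5 at k = 10, all with full credit.
- If d is less than k, the chance of catching it is d / k. A 2-minute event is credited 100% at k = 1, 2 / 5 = 40% at k = 5, and 2 / 10 = 20% at k = 10.

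Sparse logging is thus invisible to the ratio for long events, but it does lower the count of true detections for short ones.

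**The case against.** The strongest reply is that the study is exploratory and descriptive, and that its primary objective is accuracy rather than speed of detection. Section 1.4.1 itself opens by focusing on accuracy against standard monitoring. On this view, delay adds a new outcome on the strength of one rationale sentence, which rewording could settle. Part of this stands. Extremes and event counts do describe agreement to some degree, so Section 2.1 is partly addressed. It does not rescue the ratio, because counting unrelated events as detections is a fault in an accuracy measure too.

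A reader might infer three stronger claims that the documents do not support.

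- *Downloading after the procedure is itself the flaw.* It is not. Time-stamped logs can be aligned with the record afterwards. The weakness is that Section 5.2 does not plan this and no section says timestamps will be available. Nor do the documents establish that nobody looks at the devices during the procedure. Section 3.1 says only that they will be visible.
- *The study's question goes wholly unanswered.* That is too strong for the Section 2.1 objective. It is fair only for the wider question in Section 1.4.1.
- *The planned outputs can never separate a slow or sparse device from a prompt one.* Step 4 shows otherwise for events shorter than the logging interval. A sparsely logging device can also miss a true peak or trough, which the comparison of extremes could show.

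A practical objection also stands. Delay can be resolved no more finely than the record is charted. If charting were every 5 minutes (assumption), a window of one interval would be 300 seconds, and every delay in the Step 1 table would count as matched. Pairing would still remove unrelated events, as the 0.80 against 1.00 in Step 2 shows.

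**Conclusion.** The point holds as a weakness in the Section 5.2 measures, and an inexpensive improvement is available. The concordance ratio is unpaired and untimed, and the differences in extremes are untimed. Together they cannot by themselves show that a wearable performs comparably to the current monitors, although they partly describe accuracy.

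The size for this study cannot be stated, because neither the logging interval nor the charting interval is given. In the assumed mixed case the ratio reads 1.00, against 0.60 to 0.80 when events are paired, depending on the window. That no time shift changes the ratio follows from its definition and needs no assumption, provided the shifted events are still recorded within the procedure.

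**What to change.** 1. **Section 3.3.2:** at placement, record the clock of each device and the EPIC clock together and store the offset. Confirm beforehand that exported readings carry timestamps. Doing this at placement matters because Section 1.4.2 allows devices to be reused, and an offset not captured then may be unrecoverable.
2. **Section 5.2:** replace the count ratio with the proportion of charted events that have a device event of the same type within a prespecified window of one charting interval. Report it by device and event type. Count undetected events as not detected, and report unmatched device events separately. State a rule for repeated events and for values already past the cut-off at placement.
3. **Section 5.2:** describe delay by its median and 90th percentile. Allow negative values, since a device may log an event before it is charted. Note that resolution is limited to the charting interval, and state that interval.
4. **Section 1.4.1:** limit the conclusion to agreement of stored recordings, and say that live display and alarms were not tested.

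No hypothesis test is added, so the study stays descriptive. The cost is one time entry per device per subject, matching work across two devices and five event types, and probably a lower reported concordance than the ratio would give.

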1.1 Background

The term wearable technology encompasses a wide spectrum of devices worn on or near a person. (1) Market research suggests that one in five Americans are users of wearable technology with the market currently valued at over 30 billion dollars annually. (2,3) These devices have the ability to record physical information, ranging from heart rate to pulse oximetry, as well as audio and video. These devices are often marketed to improve health and well-being, and there has been significant interest in their use to diagnose, monitor and treat disease. (4) However there remain significant issues regarding the use of wearable technology (5). Rigorous studies of consumer-facing products have shown significant issues with accuracy and reliability. (6,7) Beyond simply inaccurate data, there have also been reports of unintended interference from consumer wearables, resulting in disabled clinical devices. (8) This is in addition to questions regarding the medicolegal, ethical and practical implications of recording data, audio, and video during a clinical encounter.

1.2 Investigational Device

Consumer-facing wearable smart watches are the latest in wearable watch technology and have the ability to measure heart rate, respiratory rate, single-lead electrocardiography, and blood oxygen saturation. The devices are widely available in retail stores and often advertised as the future of health. The devices have been cleared by the FDA and are already permitted inside procedure procedural areas at Mayo Clinic.

Consumer-facing wearable smart watches are the latest in wearable watch technology and have the ability to measure heart rate, respiratory rate, single-lead electrocardiography, and blood oxygen saturation. The devices are widely available in retail stores and often advertised as the future of health. The devices have been cleared by the FDA and are already permitted inside procedure procedural areas at Mayo Clinic. Additional FDA-approved accessories are available to increase the monitoring capabilities of smart devices. The QardioCore is one such accessory that allows for more detailed ambulatory electrocardiography monitoring in addition to other vital signs like skin temperature and respiratory rate.

1.3 Clinical Data to Date

Currently there is no available literature that systemically evaluates the performance of these smart devices within a controlled healthcare environment. Our study would provide the first prospective evaluation of its use in this setting.

1.4 Study Rationale and Risk Analysis (Risks to Benefits Ratio)

1.4.1 Study Rationale

We hope to further characterize and define the role of consumer-facing technology in the clinical environment by focusing on device accuracy when compared to standard clinical monitoring in patients undergoing an endoscopic procedure. We will generate and answer questions related to these devices that have not yet been explored in the gastroenterology literature. We will provide a timely and much-needed framework that addresses both practical and theoretical considerations around a technology that has become increasingly relevant to patients.

This study will specifically address whether consumer facing wearable devices can serve as patient monitoring devices in a comparable manner to the current gold standard in the procedural suite. In addition to accuracy, we will assess whether certain procedural maneuvers interfere with device data collection. This information will be relevant to patients, providers and healthcare institutions and can help inform policy regarding these devices.

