2.1 Primary Objective

Measure the accuracy of wearable technology for patient monitoring compared to currently used equipment in patients undergoing gastrointestinal endoscopic procedures with sedation

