3.4 Primary Safety Endpoints

There are no specific primary safety endpoints pertaining to the study given the non-invasive intervention. Wearable technology like smart watches and smart phones are already permitted within the procedural area.

4 Subject Selection, Enrollment and Withdrawal

All patients who are undergoing gastrointestinal endoscopic procedures with sedation may be eligible for the study. It is anticipated that we will screen up to 1000 subjects and enroll 500 subjects to the study.

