5.1 Sample Size Determination

Power analysis not performed as this study is descriptive and we do not plan to perform any statistical testing.

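### Section 1.4.1 raises comparability with standard monitoring, but the accuracy measures in 5.2 have no confidence intervals, limits of agreement or pre-specified acceptable difference

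*Combined protocol and SAP*

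**What the plan says.** Section 1.4.1 (Study Rationale) states: "This study will specifically address whether consumer facing wearable devices can serve as patient monitoring devices in a comparable manner". The yardstick it sets is a "comparable manner to the current gold standard in the procedural suite", and it adds that the information can help inform policy. The primary objective in 2.1 is worded as measurement: "Measure the accuracy of wearable technology for patient monitoring compared to currently used equipment". Section 3.1 describes a "prospective, non-blinded, exploratory study to assess the accuracy and safety of smart technology".

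Section 5.1 states: "Power analysis not performed as this study is descriptive and we do not plan to perform any statistical testing". Section 5.2 gives the general summary method: "Continuous variables will be expressed as mean and standard deviation. Categorical variables will be expressed as percentages". It then names two comparisons with the reference:

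- a concordance rate, which is the number of events on the wearable divided by the number on the anesthesia record, for five event types (tachycardia, bradycardia, desaturation, any arrhythmia, tachypnea);
- the difference between watch and sedation record in maximum and minimum heart rate, respiratory rate and oxygen saturation.

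The numerical cut-offs in 5.2 define events. None of them says how much disagreement is acceptable. Neither the Study Summary nor section 5 mentions a confidence interval, limits of agreement, a target concordance or an acceptable difference.

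**The concern.** To call two monitors comparable, one needs to know how far apart they are, how well that distance is known, and how far apart they may be. Section 5.2 supplies the first in part and leaves out the other two. If the report uses the language of 1.4.1, the reader cannot check the conclusion against anything fixed beforehand, and an acceptable difference stated once the data are in hand cannot be shown to be independent of them.

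The second risk concerns the event results. The five event types may differ widely in frequency. A percentage without an interval reads the same whether it comes from 10 events or 500. Section 1.4.1 expects institutions to use these results for policy, so it matters which figures are firm.

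**Working it through.** **The plan's own figure.** Section 4 says "we will screen up to 1000 subjects and enroll 500 subjects to the study". The 500 cannot be reproduced, because the documents give no SD, event rate, margin, power or precision target. What follows shows only the precision that 500 would give. The SDs, detection rate and event counts are all assumptions. The confidence level is 95% (z = 1.96).

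**Numeric differences.** Each patient contributes one difference per maximum or minimum, so n is the number of patients analysed.

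- Half-width for the mean difference: 1.96 × SD / √n. At n = 500 this is 0.088 SD.
- Limits of agreement: mean ± 1.96 × SD.
- Half-width for each limit: 1.96 × SD × √(1/n + 1.96² / (2(n − 1))). At n = 500 this is 0.150 SD.

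| Assumed SD | n | Mean known to | Limits of agreement | Each limit known to |
|---|---|---|---|---|
| 5 | 500 | ±0.44 | mean ± 9.8 | ±0.75 |
| 10 | 500 | ±0.88 | mean ± 19.6 | ±1.50 |
| 15 | 500 | ±1.31 | mean ± 29.4 | ±2.25 |
| 5 | 250 | ±0.62 | mean ± 9.8 | ±1.06 |
| 15 | 250 | ±1.86 | mean ± 29.4 | ±3.18 |

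The rows for 250 are there because 5.2 leaves subjects with missing or incomplete data out of the final analysis and gives no expected rate; 250 is only an example. Precision is not the main difficulty for these measures. The mean is tightly known, yet individual disagreement could span about 10 or about 30 units either side of it. Only an acceptable difference can say which of these counts as comparable.

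**Event detection.** The Wilson interval for x of m reference events, with p = x/m, is [p + z²/(2m) ± z√(p(1 − p)/m + z²/(4m²))] / (1 + z²/m). It assumes independent events, each matched between device and record.

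- 20 of 25: centre (0.8 + 0.0768)/1.1537 = 0.760, half-width 0.151, giving 60.9% to 91.1%.
- 8 of 10: centre (0.8 + 0.1921)/1.3841 = 0.717, half-width 0.227, giving 49.0% to 94.3%.
- 400 of 500: 76.3% to 83.3%.

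At one event per affected patient, 25 and 10 events correspond to 5% and 2% of 500 patients. All three results would appear as 80%. The number of reference events sets the precision, not the 500 enrolled.

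**Why the planned ratio cannot simply be given this interval.** Section 5.2 divides one count by another and does not say that the events must be the same ones. Take an invented case with 10 events on the record, of which the device catches 8. If the device also reports 2 that are not on the record, the ratio is 10/10 = 100%; if it reports 4 such events, it is 12/10 = 120%. Matched detection is 8/10 = 80% in both cases. The count ratio can exceed 100% and is not a binomial proportion, so an interval on it would not show accuracy.

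**The case against.** The strongest reply is that the study is exploratory and descriptive, that its primary objective in 2.1 is already an estimation aim, and that the comparability sentence sits in the rationale and not among the objectives. All of this stands. A descriptive study needs no hypothesis test or power calculation, and their absence is not a fault here. It does not answer the point, though: with no test planned, the interval is what shows how far an estimate can be trusted.

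A reader might infer that the study undertakes to decide comparability. The text says it will address the question and commits to no yes-or-no declaration. A reader might also infer that only means, SDs and percentages are planned. That overlooks the two direct comparisons in 5.2.

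It is also fair to say that a conclusion would not be without any basis. If the general mean-and-SD rule is applied to the paired differences and n is given, a reader can derive a confidence interval and limits of agreement for each vital sign. Nothing says that event counts will be withheld. What stands is that 5.2 does not require any of this, and that an acceptance limit set in advance cannot be recovered later.

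**Conclusion.** The point holds as a mismatch between the question in 1.4.1 and the analysis in 5.2. A comparability conclusion would have no pre-specified basis, and weak rare-event results would not be recognisable as weak. The documents do not support the stronger readings that the plan promises a verdict, that the data could say nothing about agreement, or that 500 patients are too few.

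Its practical size is small for the numeric differences and potentially large for rare events, where an interval could run from about half to over nine-tenths. These sizes rest on assumed SDs, detection rate and event counts, and on matched, independent events; the mismatch itself depends on none of them. Data collection is not affected. What is affected is how far the main conclusion can be taken.

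**What to change.** In 5.2:

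- For each vital sign, report the mean paired difference and the 95% limits of agreement for the maximum and for the minimum, each with a 95% confidence interval.
- For each event type, report numerator, denominator and a 95% confidence interval, calculated on device events matched to record events under a stated matching rule. Allow for clustering by patient where a patient has several events.

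In 1.4.1, word the aim as estimating agreement with standard monitoring, in line with 2.1. If the sponsor prefers to keep the word comparable, it should enter its own acceptance limits in 5.2 before the first data download and tie the claim to the intervals.

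The cost is protocol wording and slightly more analysis, including the event matching, with no added patients. The downside is that rare-event results will be visibly imprecise.
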